## 8.7. Data Analysis

Data analysis will be performed by Gilead Sciences. Internal independent biostatistician and/or epidemiologist will perform the propensity score model with access to the baseline data only. No outcome data will be provided to them.

### 8.7.1. Analysis Sets

The Full Analysis Set (FAS) will include all enrolled patients who took at least 1 dose of AZA.

The Effectiveness Evaluable Analysis Set (EEAS) will include all FAS patients who had at least one response assessment or with a documented death after the index date.

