| Data Analysis: | 
Continuous variables will be summarized by mean, standard deviation, median, 25% quantile, 75% quantile, minimum and maximum. Categorical variables will be summarized by number and percentage of patients in each categorical definition including 95% CIs. Time-to-event endpoints will be described using the Kaplan-Meier method. The Full Analysis Set (FAS) includes all enrolled patients who took at least 1 dose of AZA. The Effectiveness Evaluable Analysis Set (EEAS) includes all FAS patients who had at least 1 response assessment or died after the index date.
 
The effectiveness analyses (except DCR, real-world duration of complete remission [rw-DCR], DOR, and real-world duration of response [rw-DOR]) will be performed on the FAS. DCR and rw-DCR will be evaluated using FAS patients who achieve a CR and rw-CR, respectively. DOR and rw-DOR will be evaluated using FAS patients who achieve an objective response (OR) and real-world objective response (rw-OR), respectively. Sensitivity analyses will be performed for the primary and secondary endpoints (except DCR, rw-DCR, DOR, and rw-DOR) using EEAS.
 
Details of analytical comparison with magrolimab and AZA combination therapy trial (5F9005) data will be included in the statistical analysis plan.
 |
| Milestones:    | Start of data collection: first quartile (Q1) 2021
Interim and Progress report: Not Applicable
End of Data collection: first quartile (Q1) 2021
Final Study report: third quartile (Q3) 2021  |

---

This study will be conducted in accordance with the guidelines of Good Pharmacoepidemiology Practices (GPP) including archiving of essential documents.

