### 8.1.2. Secondary Endpoints

**Real -World Complete Remission (rw-CR) Rate** is defined as the proportion of patients who achieve a CR as documented within their EHRs with or without confirmation of corresponding BM and peripheral blood parameters as defined per IWG 2006 MDS response criteria, during the treatment period with AZA or prior to the initiation of next MDS treatment.

**Objective Response Rate (ORR)** is defined as the proportion of patients who achieve a CR, or PR as documented within their EHRs with confirmation of corresponding BM and peripheral blood parameters as defined per IWG 2006 MDS response criteria, or achieve an mCR or HI, during the treatment period with AZA or prior to the initiation of next MDS treatment.

**Real -World Objective Response Rate (rw-ORR)** is defined as the proportion of patients who achieve a CR, or PR, as documented within their EHRs with or without confirmation of corresponding BM and peripheral blood parameters as defined per IWG 2006 MDS response criteria, or achieve an mCR or HI, during the treatment period with AZA or prior to the initiation of next MDS treatment.

**Duration of CR (DCR)** is defined as the interval from the first EHR documentation of a CR with confirmation of corresponding BM and peripheral blood parameters as defined per IWG 2006 MDS response criteria to the earlier of the first documentation of relapse, disease progression, or death from any cause.

**rw-DCR** is defined as the interval from the first EHR documentation of a CR with or without confirmation of corresponding BM and peripheral blood parameters as defined per IWG 2006 MDS response criteria to the earlier of the first documentation of relapse, disease progression, or death from any cause.

**Duration of Response (DOR)** is defined as the interval from when the criteria are first met for OR to the earlier of the first documentation of relapse, disease progression, or death from any cause.

**rw-DOR** is defined as the interval from when the criteria for rw-OR are first met to the earlier of the first documentation of relapse, disease progression, or death from any cause.

**Progression -Free Survival** is defined as the interval from the date of initiation of AZA to the earlier date of the first documentation of relapse, disease progression or death from any cause.

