**Time to the next treatment** is defined as the interval from the date of initiation of treatment with AZA to the earlier date of the initiation of next anti-leukemic treatment of MDS (excluding palliative care or palliative radiation) or death from any cause.

**Overall Survival** is defined as the interval from the date of initiation of AZA to death from any cause.

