### 8.7.4. Effectiveness Analyses

For the primary effectiveness analysis, CR rates will be evaluated using the FAS. The point estimate and the corresponding 95% CIs based on the Clopper-Pearson exact method will be provided. The same method will be applied to rw-CR, ORR, and rw-ORR using the FAS.

The time-to-event effectiveness endpoints including PFS, DCR, rw-DCR, DOR, rw-DOR, TTNT, and OS will be analyzed using the Kaplan-Meier method. Kaplan-Meier curves will be provided for the time-to-event endpoints. The endpoints of PFS, TTNT, and OS will use FAS. DCR and rw-DCR will include the FAS patients who achieve a CR or rw-CR, respectively. DOR and rw-DOR will include the FAS patients who achieve an OR or rw-OR, respectively.

CCI

Sensitivity analyses will be performed for the primary and secondary endpoints (except DCR, rw-DCR, DOR, and rw-DOR) using EEAS.

The results of this study will be compared to the ongoing Phase 1b single -arm study of magrolimab + AZA (Study 5F9005) in patients with untreated higher-risk MDS. A detailed statistical analysis for comparison will be described in the statistical analysis plan.

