Death information is updated weekly in the LADMF and is as current as it is reported to the Social Security Administration. However, death dates recorded in the LADMF are not complete due to limitations on access to records for research purposes {Navar 2019}. LADMF and hospital death records were compared after access restrictions imposed in 2011 {Levin 2019}. After 2011, LADMF sensitivity for in-hospital deaths was 14.8% (compared with 88.9% before 2011) and 28.9% for out-of-hospital deaths (compared with 71.4% before 2011). The LADMF specificity, however, was greater than 99% both prior to and after 2011. Peters and colleagues (2017) compared capture of death dates in the LADMF with a multi-phased approach that assessed online databases (including LADMF), EHR records, and provider follow-up {Peterss 2017}. The authors reported that 42.7% of death records were identified by the LADMF, and the remainder were identified from another online database (32.6%), EHR records (22.2%), and provider follow-up (3.5%). Overall, the sensitivity was 58.5%, with 100% specificity.

In a study of the iKM EHR database and LADMF, it was observed that 93.3% of all death records were captured in structured fields and 6.7% of death records were solely identified by the LADMF. Among deaths recorded by both structured data and the LADMF, concordance was 88.0%. When both structured and unstructured data are available, 99.4% of death records are captured from these sources, with 0.6% of death records solely identified by the LADMF. Between 2015 and 2019, the proportion of death records captured by structured data trended upward (slope = 4.04).

Based on previous studies of other solid tumors, it is estimated that physician-assessed response will be available for greater than 60% of patients in the RWD. However, this may be impacted by BM reports and may vary considerably for patients with MDS. In standard clinical practice in the treatment of MDS, bone marrow biopsies are not routinely performed other than during diagnosis and at suspected disease progression. If BM biopsy results are unavailable for a significant proportion of patients, this will lead to an underestimate of the CR and PR rate (as defined in the Table 8-1) in the study. Therefore, the interpretation of data collected and analysed retrospectively will be dependent on the completeness and quality of the data.

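### The EEAS admits patients because they died, so the planned EEAS sensitivity analysis of OS can only lower the curve; PFS and TTNT are also selected on death, in a direction the protocol does not settle

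*Protocol*

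**What the plan says.** Section 8.7.1 of the protocol defines the EEAS as "all FAS patients who had at least one response assessment or with a documented death after the index date". The synopsis, under Data Analysis, gives the same rule: the set "includes all FAS patients who had at least 1 response assessment or died after the index date". Neither text limits how long after the index date the death may occur.

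Section 8.7.4 assigns the main time-to-event analyses to the FAS: "The endpoints of PFS, TTNT, and OS will use FAS". It then adds: "Sensitivity analyses will be performed for the primary and secondary endpoints (except DCR, rw-DCR, DOR, and rw-DOR) using EEAS". The synopsis repeats this. Only the four duration endpoints are exempt, so OS, PFS and TTNT are to be analysed on the EEAS as well.

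Death is an event in all three (Section 8.1.2). OS "is defined as the interval from the date of initiation of AZA to death from any cause". PFS runs to the "earlier date of the first documentation of relapse, disease progression or death from any cause". TTNT runs to "the earlier date of the initiation of next anti-leukemic treatment of MDS (excluding palliative care or palliative radiation) or death from any cause".

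On how many patients will have an assessment, Section 8.10 says "it is estimated that physician-assessed response will be available for greater than 60% of patients in the RWD". It adds that this experience comes from solid tumours and may differ considerably in MDS.

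**The concern.** A patient without a response assessment enters the EEAS by dying and stays out by living. For OS, membership is therefore decided partly by the outcome itself, at any point in a follow-up of 1 to 7 years. A Kaplan-Meier curve on such a set does not estimate survival in any population that could be defined at the index date.

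The group at risk of exclusion may be large, because up to about 40% of patients could lack an assessment on the protocol's own estimate. The result would be reported as a sensitivity analysis. A reader would take a difference from the FAS as information about robustness, when part or all of it comes from the way the set was built.

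**Working it through.** **Inputs from the protocol.** Median OS on azacitidine about 13 months (Section 6.1). Index dates from 01 January 2014 to 01 January 2020 and data cut at 01 January 2021 (Sections 8.2 and 8.2.1), so administrative follow-up is 12 to 84 months. Response assessment in more than 60% (Section 8.10). The protocol gives no figure for the size of the EEAS or for survival on it, so there is none to reproduce.

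**Assumptions.** Exponential survival, uniform accrual, 60% assessed unless stated otherwise. The loss-to-follow-up rate is not in the protocol; 0% and 2% per month are used.

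**Step 1: direction for OS.** The Kaplan-Meier estimate is S(t) = ∏(1 − d_j/n_j), with d_j deaths and n_j at risk at each death time. The EEAS drops only patients with no documented death, so every d_j is unchanged. If m_j ≥ 0 dropped patients were still at risk, the factor becomes 1 − d_j/(n_j − m_j), which is at most 1 − d_j/n_j. Each factor stays equal or falls. This needs no assumption about assessment or loss.

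**Step 2: how many are dropped (no loss, assessment independent of survival).**
- λ = ln 2/13 = 0.0533 per month.
- Share alive at the cut = (e^(−12λ) − e^(−84λ))/(72λ) = (0.527 − 0.011)/3.839 = 0.134, so about 87% die.
- Dropped = 0.40 × 0.134 = 0.054. The EEAS is about 95% of the FAS.

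**Step 3: size for OS.** Simulated Kaplan-Meier medians, true median 13.0 months. In the independent model, assessment has no relation to survival. In the accrual model, it occurs at a constant rate over each patient's follow-up, calibrated to the stated overall share.

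| Assessed | Loss | Independent | Accrual |
|---|---|---|---|
| 60% | none | 12.0 | 12.6 |
| 60% | 2%/month | 11.1 | 12.1 |
| 80% | none | 12.5 | 12.9 |
| 80% | 2%/month | 12.0 | 12.8 |

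In the independent model with 60% assessed, 36-month OS falls from 14.6% to 11.6% without loss, and 12-month OS from 52.7% to 47.2% with 2% monthly loss. If the true median were 18 months (assumed), the independent-model EEAS median would be 15.9 months without loss and 14.7 with it.

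**Step 4: PFS and TTNT.** Here the dropped patients are alive but not necessarily event-free. A living unassessed patient may have started next treatment, which is a TTNT event. Such a patient may also have met progression through a haemoglobin fall or transfusion dependence (Table 8-1). Assumptions: 60% assessed independently of survival, 10% yearly loss, median 15 months to next treatment and 10 months to progression.
- TTNT median: 6.9 months on FAS, 6.5 on EEAS. If unassessed patients switch at twice the rate of others, 5.9 and 5.8. At four times the rate the order reverses: 4.8 and 4.9.
- PFS median: 7.6 and 6.7 if progression is seen only in assessed patients; 5.6 and 5.4 if laboratory values also reveal it; 6.7 and 6.7 if living unassessed patients are censored at the index date.

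**Step 5: what the death clause does for response rates.** Take a 15% CR rate on the FAS with all responders assessed. On the EEAS as written (Step 2) it is 15/0.946 = 15.9%. Without the death clause, on assessed patients only, it is 15/60 = 25%. In the accrual model without loss, median OS in an assessed-only set is about 20.6 months against a true 13.0, because patients must survive long enough to be assessed.

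**The case against.** The size is uncertain and may be small. In a chart review, patients followed longer have more visits at which to be assessed. The unassessed are then largely early deaths, whom the EEAS keeps; the accrual column shows the shift shrinking to between 0.1 and 0.4 months without loss. The protocol expects more than 60% assessed, and the 2% monthly loss has no source in it. Even a 1.0-month shift lies within the sampling range of the FAS median at n = 400, simulated at about 11.3 to 14.9 months. All of this stands as a limit on magnitude. It does not answer the point on direction: both curves come from the same patients, and the difference for OS cannot have the opposite sign in any sample.

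Three stronger readings are tempting, and the protocol does not support them.
- A reader might infer a downward bias for all three endpoints. It is proven only for OS. Step 4 shows PFS curves that coincide and TTNT curves that cross over, although the TTNT reversal needed an extreme scenario. PFS censoring rules may lie in a statistical analysis plan that is not shown.
- A reader might infer that the comparison with Study 5F9005 is tilted towards the combination. Nothing says the EEAS enters that comparison, which is deferred to a separate plan.
- A reader might infer that the death clause itself is the error and should go. For response rates it does useful work, keeping unassessed deaths as non-responders. Removing it would inflate CR (Step 5) and select on survival to assessment.

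Nor is it an error that the EEAS may be close to the FAS for CR; how close depends on mortality and loss.

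**Conclusion.** The point holds in a limited form. As written, the protocol orders an OS sensitivity analysis on a set selected partly by death, and its curve can only equal or fall below the FAS curve. At the protocol's 13-month median with 60% assessed, the EEAS median is about 12.0 to 12.6 months without loss and about 11.1 to 12.1 with an assumed 2% monthly loss. The range reflects how assessment relates to survival, which the protocol does not state. PFS and TTNT are also selected on death, with direction and size left open.

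The primary CR analysis and the main OS, PFS and TTNT analyses use the FAS and are unaffected. What is at stake is a biased secondary result being read as a check on robustness.

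**What to change.** In Section 8.7.4 and in the Data Analysis part of the synopsis, add OS, PFS and TTNT to the endpoints exempt from the EEAS sensitivity analyses. Those analyses then cover only CR, rw-CR, ORR and rw-ORR, and OS, PFS and TTNT are reported on the FAS alone. Leave the EEAS definition in Section 8.7.1 as it is, so that unassessed deaths stay in the denominator as non-responders.

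The cost is one edited sentence in each of two places and three fewer sensitivity analyses. No data collection changes, and no valid information is lost.

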### 8.7.2. Demographic and Baseline Characteristics

Continuous variables will be summarized by mean, standard deviation, median, 25% quartile, 75% quartile, minimum, and maximum. Categorical variables will be summarized by number and percentage of patients in each categorical definition including 95% CIs.

Demographic and baseline measurements will be summarized using standard descriptive methods and FAS. Demographic summaries will include age, sex, race/ethnicity, and geographic location. Baseline characteristics will include a summary of body weight, height, and body mass index. Baseline disease characteristics summaries will include but are not limited to IPSS-R score, MDS histological classification, ECOG score, and cytogenetics. Any Karnofsky performance score will be converted to ECOG {[Center for International Blood & Marrow Transplant Research \(CIBMTR\) 2009](#)}.

### 8.7.3. Safety Analyses

There are no safety analyses in this study.

### 8.7.4. Effectiveness Analyses

For the primary effectiveness analysis, CR rates will be evaluated using the FAS. The point estimate and the corresponding 95% CIs based on the Clopper-Pearson exact method will be provided. The same method will be applied to rw-CR, ORR, and rw-ORR using the FAS.

The time-to-event effectiveness endpoints including PFS, DCR, rw-DCR, DOR, rw-DOR, TTNT, and OS will be analyzed using the Kaplan-Meier method. Kaplan-Meier curves will be provided for the time-to-event endpoints. The endpoints of PFS, TTNT, and OS will use FAS. DCR and rw-DCR will include the FAS patients who achieve a CR or rw-CR, respectively. DOR and rw-DOR will include the FAS patients who achieve an OR or rw-OR, respectively.

CCI

Sensitivity analyses will be performed for the primary and secondary endpoints (except DCR, rw-DCR, DOR, and rw-DOR) using EEAS.

The results of this study will be compared to the ongoing Phase 1b single -arm study of magrolimab + AZA (Study 5F9005) in patients with untreated higher-risk MDS. A detailed statistical analysis for comparison will be described in the statistical analysis plan.

## **8.8. Quality Assurance and Quality Control**

In Stage 2, Gilead and/or McKesson will conduct quality checks in order to ensure quality and integrity of the data.

Major quality assurance steps are briefly described below:

- **Training:** Qualified and experienced chart abstractors will extract data from EHR systems and will be further trained on study -specific protocol and procedures including understanding of MDS and key clinical variables. Chart abstractors will be provided the Standard Operating Procedure or Study Handbook for guidance and reference.
- **Reliability:** Ten (10) charts will be distributed among all planned abstractors to be independently extracted twice and evaluated for inter-abstractor differences. A resolution session will be arranged for all abstractors as part of their training.
- **eCRF and validation rules:** To minimize errors in data transfer and data entry, all patient level information will be directly collected into an eCRF with built-in logic checks for variables with limits or out of bound value restrictions. Further, automated alerts will be built in to prevent potentially erroneous, incomplete, or inconsistent data.
- **EDC:** Data will be stored within McKesson's EDC system. The EDC system maintains records of changes to capture data overwriting or edits. Limited study personnel will be granted access to the EDC.
- **Algorithm development:** Algorithms will be developed to derive composite study variables or outcomes from multiple clinical and/or laboratory parameters to avoid manual interpretation. These algorithms will be reviewed by a board-certified hematologist and tested repeatedly for accuracies.

Major quality control steps are briefly described here:

- **Random data check:** At least 13% of randomly selected patient records will be checked for completeness, correctness, and consistencies. Sampling of charts for QC is based on the assumption of 90% chart accuracy, at 80% confidence, with a sampling error of 5%, based on binomial distribution of chart accuracy (yes/no). For 400 qualified charts, the number of charts for QC based on the calculation is 52.
- **Source data verification:** Pre-defined list of variables from patient records undergoing random data checks as described above will be verified for correctness from the original source chart.

- Algorithm validation check: Results from algorithms will be randomly checked for accuracy. Algorithms will be validated before applying to stage 2 chart data. Using stage 1 data, 10 patients will be randomly chosen, and results from the algorithms will be checked for the accuracy of derivation of the response endpoints.
- Outcome measure quality improvement: Clinical outcomes for MDS involves measurement of multiple clinical and laboratory parameters. To ensure complete and correct response assignment for patients, all responses meeting the CR, rw-CR, PR, and rw-PR will be subject to adjudication by an independent assessor who will be a board-certified hematologist.
- Aggregate data quality check: Periodic data quality check for missing values, inconsistencies, and completeness will be performed on aggregate data to date during and at the end of the data collection period.

### **8.9. Independent Adjudication of Responses**

All response assessments meeting the protocol definitions of CR, rw-CR, PR, and rw-PR will be examined and adjudicated by an independent assessor who is a board-certified hematologist who specializes in the treatment of MDS. This assessor will be employed by McKesson with no direct Gilead involvement.

### **8.10. Limitations of the Research Methods**

This study has the characteristic disadvantages of retrospective studies; for example, selection bias, information bias, misclassification bias, and history bias. To reduce selection bias, patients' eligibility criteria have been well defined in the protocol. A selection bias is introduced by the choice of healthcare providers that contribute their EHRs to USON's iKM EHR. This is mitigated by the fact that there is significant geographic dispersion within USON with all regions of the country receiving some coverage in the system. Overall, the iKM EHR system captures data on approximately 10% of patients with newly diagnosed cancer in the US. Approximately 1,200 physicians are affiliated with USON, operating in more than 470 cancer treatment center locations across the US. Each year, more than 1 million patients with cancer are treated within the USON database.

The total MDS patient pool that meets preliminary eligibility criteria for this study is in excess of 11,000 patients, which further reduces selection bias.

Information bias is prevented by using standard measurement instruments, including the use of eCRF and appropriate training of RWD partner personnel entering the data. The standards of training provided will be described under the Training Manuals of McKesson Life Sciences and will be available for inspection. Quality Assurance and Quality Control process for each database vendor will be described in the respective Service Agreement/Work Practice and will be available for inspection. There is minimal risk of history bias in this study as the standard of care for the first-line treatment of MDS has not changed over the Study Index Period. This study relies on a retrospective chart review of EHR. The EHR contains information pertaining to

managing patients in clinical practice rather than for research purposes. This may impede the standardization of the data collection methods and instruments and the reporting practices of the physician. Secondly, RWD databases are subject to coding errors. Problems with inadequate or inaccurate codes in the databases may introduce some level of misclassification bias in the study. Likewise, some variables of interest may not be as complete across the entire study population. Thirdly, each database has a close link to a dedicated network (McKesson Life Sciences USON) and, therefore, contains information on patients only when they are seen by physicians within that network. As such, services and procedures provided outside of the network (eg, emergency hospitalizations) are not captured by the database, including drugs received by patients from pharmacies not affiliated with the same network.

Misclassification of primary endpoints will be mitigated by use of complete ascertainment of all IWG response criteria and independent adjudication by a qualified hematologist employed by McKesson with no direct Gilead involvement.

Patient treatment history prior to the first encounter at a practice within the network may only be available in physician progress notes and may not be well captured or only partially captured in the EHR. Similarly, oral therapies are recorded in or prescribed through EHR-related systems, but fulfillment is not observable. In this study, attempts will be made to confirm receipt of oral therapies through chart review to help mitigate this potential limitation.

Death data are relatively complete. The primary source of death information will be structured and unstructured records of death in the iKM EHR database. McKesson has certification to access the LADMF of the Social Security Administration and, as such, this will be a supplementary source of vital (death) records in addition to the NDI of the Centers for Disease Control. Common patient identifiers (patient ID, name, and birth date) will be used to link patients from the iKM data warehouse and iKM chart review. The social security number (SSN) will be used to link patients from iKM and LADMF data sources. All patients within iKM are assigned a unique patient identifier by iKM version (eg, some large practices have separate installations by location). When linking to the LADMF, patient SSN is used. Some practices do not collect SSN and some patients may not report it.

Death information is updated weekly in the LADMF and is as current as it is reported to the Social Security Administration. However, death dates recorded in the LADMF are not complete due to limitations on access to records for research purposes {Navar 2019}. LADMF and hospital death records were compared after access restrictions imposed in 2011 {Levin 2019}. After 2011, LADMF sensitivity for in-hospital deaths was 14.8% (compared with 88.9% before 2011) and 28.9% for out-of-hospital deaths (compared with 71.4% before 2011). The LADMF specificity, however, was greater than 99% both prior to and after 2011. Peters and colleagues (2017) compared capture of death dates in the LADMF with a multi-phased approach that assessed online databases (including LADMF), EHR records, and provider follow-up {Peterss 2017}. The authors reported that 42.7% of death records were identified by the LADMF, and the remainder were identified from another online database (32.6%), EHR records (22.2%), and provider follow-up (3.5%). Overall, the sensitivity was 58.5%, with 100% specificity.

In a study of the iKM EHR database and LADMF, it was observed that 93.3% of all death records were captured in structured fields and 6.7% of death records were solely identified by the LADMF. Among deaths recorded by both structured data and the LADMF, concordance was 88.0%. When both structured and unstructured data are available, 99.4% of death records are captured from these sources, with 0.6% of death records solely identified by the LADMF. Between 2015 and 2019, the proportion of death records captured by structured data trended upward (slope = 4.04).

Based on previous studies of other solid tumors, it is estimated that physician-assessed response will be available for greater than 60% of patients in the RWD. However, this may be impacted by BM reports and may vary considerably for patients with MDS. In standard clinical practice in the treatment of MDS, bone marrow biopsies are not routinely performed other than during diagnosis and at suspected disease progression. If BM biopsy results are unavailable for a significant proportion of patients, this will lead to an underestimate of the CR and PR rate (as defined in the Table 8-1) in the study. Therefore, the interpretation of data collected and analysed retrospectively will be dependent on the completeness and quality of the data.

